- **MRU Assessment (Weeks 1 – 12, Follow-Up Weeks 1 & 2)**

As applicable, the site will document the following for the subject's previous visit week:

- Any and all DRG Codes, using ICD-10, that were or would be applied to the subject
- The associated CPT codes and modifiers for those CPT codes

- **Concomitant Medications (All Study Visits)**

Sites will query the subjects at each visit about any medications they are currently taking. Only medications that (1) affect the wound area, (2) affect the limb, (3) are related to the treatment of the wound, (4) are being used to treat any AEs that develop during this study, will be documented. The name, indication/reason for use, dose, route, frequency, start/stop date, and whether the medication is being used to treat any adverse events will be noted.

- **Assessment of Adverse Events (All Study Visits after Screening Visit 1)**

After the initial screening visit, sites will report full information on those AEs possibly, probably, or definitely-related to the investigational product or study procedure. Other AEs that are not related or unlikely related will only have basic information collected (Stop and Start Date). If these AEs change in relationship (e.g., an ongoing unrelated AE becomes possibly related) full information will be collected.

Sites will collect the AE onset date and a description of the event. The sites will then make a determination as to whether the AE is Serious or not and will grade its severity marking it as either (1) mild, (2) moderate, or (3) severe. For any treatment or procedure-related SAEs that are graded as (1) possibly, (2) probably or (3) definitely-related, the site will also indicate whether the event is anticipated or unanticipated. Definitions of these terms can be found in the following section of the protocol.

Sites will also note the action taken (none, medication given, hospitalization required, surgical intervention, or other), and the outcome of the AE (resolved with or without sequelae, death, ongoing, or other). If available, an adverse event resolution date will be noted. The site will also make a determination as to whether the AE caused the subject to discontinue participation in the study.

See Section 8.3 below for more information on AE definitions and procedures.

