8.3 ADVERSE EVENTS AND SERIOUS ADVERSE EVENTS

8.3.1 DEFINITION OF ADVERSE EVENT (AE)

For the purposes of this research protocol, an **adverse event** means any untoward medical occurrence or adverse reaction (AR) associated with the use of an intervention in humans, that is considered possibly, probably, or definitely-related to the investigational product or study procedure. All events starting or worsening after the first randomized treatment through study exit will also be collected.

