8.3.9 SERIOUS ADVERSE EVENT REPORTING

Investigators are instructed to report SAEs to Integra within 10 business days of the Investigator becoming aware of the SAE.

SAEs must be reported by the Investigator to Integra by completing the SAE eCRF. All SAEs and deaths that are possibly related, probably related, or definitely related to the investigational product or study procedures must be reported. The information collected will include a minimum of the following: subject number, a narrative description of the event, lot number of device used on subject, and an assessment by the Investigator as to the intensity of the event and relatedness to study device. Follow-up information on the SAE may be requested by the Sponsor.

Any subjects reporting SAEs that have not resolved by their last treatment visit will be followed via phone or clinic visit through resolution or 14 days post final visit, whichever comes first.

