10.6. Safety Analysis

Safety will be assessed through reports of adverse events and serious adverse events. Adverse Events related to the device, study ulcer and/or study procedures and all Serious Adverse Events will be recorded.

All safety parameters will be summarized descriptively by treatment. No inferential statistics are planned.

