10.7. Adverse Events

Adverse events will be coded using the MedDRA Medical Dictionary. Treatment Emergent AE's (TEAE) are defined as events with an onset on or after the first randomized treatment. TEAEs will be summarized by treatment group, System Organ Class, and preferred term. The following TEAE summaries will be provided:

- TEAEs by severity grade
- TEAEs by relationship to study treatment.

In addition, separate summaries of serious adverse events, and adverse events resulting in discontinuation of study treatment will be presented.

The safety population will be used for the safety analyses. Summary will be provided by subject and by adverse events. Subjects will be counted only once for subject-based analysis.

Confidential Page 18 of 23

If the same event changes in severity for a subject, the worst severity will be reported. Subjects could be counted more than once for AE-based analysis, all AEs will be reported for AE-based analysis.

An adverse event is considered to be treatment emergent if (1) it was not present when the active phase of the study began, and it is not a chronic condition that is part of the subject's medical history; or (2) it is present at the start of the study or as part of the subject's medical history, but the severity or frequency increased during the active phase. The active phase of the study begins on the day of the first dose of test article and the last dose of test article.

Treatment-emergent adverse events (TEAE) will be summarized for each treatment group by body system and preferred term. The severity of all adverse events will be determined by the investigator's judgment and classified as mild, moderate or severe.

Treatment groups will be compared with respect to the incidence of adverse events (all and TEAEs) and the proportion of subjects withdrawing from the study for adverse events by reason of withdrawal. Comparisons will be made overall, by body system and by preferred term and will be further categorized by severity and by study drug relationship.

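### The AE and SAE collection rules contradict each other and the planned safety outputs; if Protocol 8.2's dates-only rule governs, events judged unrelated cannot be coded or graded

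*Protocol*

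**What the plan says.** **Adverse events.** Protocol 8.2 (Assessment of Adverse Events) sets two levels of detail. For the first, "sites will report full information on those AEs possibly, probably, or definitely-related to the investigational product or study procedure". For the rest, "Other AEs that are not related or unlikely related will only have basic information collected (Stop and Start Date". It adds that full information will be gathered if an event's relationship later changes. The next paragraph starts "Sites will collect the AE onset date and a description of the event" and goes on to seriousness and severity; the one after asks for action taken and outcome. Neither states a relatedness limit, except that the anticipated/unanticipated item applies to related SAEs only.

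Protocol 8.3.1 defines an adverse event as one "that is considered possibly, probably, or definitely-related to the investigational product or study procedure", then says "All events starting or worsening after the first randomized treatment through study exit will also be collected". Protocol 8.3.7 says all AEs are captured, but refers back to 8.2 for how.

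**Serious adverse events.** The protocol synopsis and SAP 10.6 have no relatedness limit: in the SAP, "all Serious Adverse Events will be recorded". Protocol 8.3.9 opens with an unrestricted instruction to report SAEs, then says "All SAEs and deaths that are possibly related, probably related, or definitely related to the investigational product or study procedures must be reported". The first sentence of Protocol 9.4.7 speaks only of AEs and SAEs related to product, study ulcer or procedures.

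**Planned outputs.** SAP 10.7: "TEAEs will be summarized by treatment group, System Organ Class, and preferred term". It adds tables by severity and by relationship, separate SAE summaries, and between-arm comparisons of incidence overall, by body system and by preferred term. None is limited to related events.

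**The concern.** A preferred term needs a description of the event, and a severity table needs a grade. Two dates supply neither. If sites follow the dates-only sentence, the SAP's tables of all treatment-emergent events by term and severity can include only events that someone called related.

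That call is made at the site in a trial that Protocol 6.3 describes as open label. Under Protocol 8.3.2 and 8.3.3, an event in a product arm can be related through the product or through a study procedure. An event in the standard-of-care arm has only the procedure route. The share called related could therefore differ by arm even when true event rates do not.

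For SAEs the stake is completeness. A site that follows the mandatory-reporting sentence of 8.3.9 could leave out a death it judged unrelated, while the SAP assumes that every SAE is in the database.

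**Working it through.** There is no stated figure to reproduce. The check compares what is collected with what is planned.

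**1. Which fields exist for an event judged not or unlikely related?**

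| Field | Dates-only sentence of 8.2 governs | Later paragraphs of 8.2 cover every AE | Planned use |
|---|---|---|---|
| Start and stop date | yes | yes | treatment-emergent status |
| Related or not | yes, it puts the event in this group | yes | table by relationship |
| Description | no | yes | System Organ Class, preferred term |
| Severity | no | yes | table by severity |
| Seriousness | no | yes | SAE summary |
| Action and outcome | no | yes | listings of complications in Protocol 9.4.7 |

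On the first reading, a crude count of events after first treatment is still possible, but nothing by term or grade.

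**2. Which reading does the text favour?** The clause giving full information to an event whose relationship changes has a purpose only if full information was not gathered before. That favours the dates-only reading. Against it, the anticipated/unanticipated item is expressly limited to related SAEs, a limit that would be largely redundant if the whole paragraph already covered related events only. The second sentence of 8.3.1 calls for all events after first randomized treatment but does not say with which fields. The text does not settle the matter.

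**3. SAEs.**

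| Place | Scope |
|---|---|
| Protocol synopsis, Safety Assessment | all SAEs |
| SAP 10.6 | all SAEs |
| Protocol 8.3.9, first sentence | SAEs, no limit |
| Protocol 8.3.9, mandatory-reporting sentence | related SAEs and deaths |
| Protocol 9.4.7, first sentence | related AEs and SAEs |

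Three places are unrestricted and two are restricted. The conflict lies partly within one section.

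**4. What could the dates-only rule do to a table by term or severity?** The documents give no AE rates or relatedness shares, so this illustration uses assumed values. Let r be the true AE risk, equal in both arms, and s the share called related. The tabulated proportion is r × s. The planned arm size is 38 (Protocol 9.2, SAP 5).

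| True risk r | s, product arm vs standard of care | Tabulated | False gap | Subjects of 38 |
|---|---|---|---|---|
| 20% | 60% vs 20% | 12% vs 4% | 8 points | 4.6 vs 1.5 |
| 40% | 60% vs 20% | 24% vs 8% | 16 points | 9.1 vs 3.0 |
| 60% | 60% vs 20% | 36% vs 12% | 24 points | 13.7 vs 4.6 |
| 20% to 60% | 40% vs 20% | 8–24% vs 4–12% | 4 to 12 points | 3.0–9.1 vs 1.5–4.6 |
| 20% to 60% | 30% vs 30% | 6–18% in both | 0 | 2.3–6.8 in both |

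The gap is r × (s in the product arm − s in the standard-of-care arm). Its size and sign depend on a difference that the documents do not give. With equal shares of 30% there is no gap, but both arms are under-counted by 1 − 0.30 = 70%.

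**The case against.** A reader might infer that the SAP's tables cannot be built without bias, or that the protocol hides unrelated SAEs. The documents support neither.

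- The later paragraphs of 8.2 can be read as covering every AE, and the eCRF, which would settle it, is not in the documents. This stands: the text is contradictory, not clearly restrictive.
- It may seem that dates-only events cannot be tabulated by relationship. They can, because the relationship call is what puts them in that group. Term, severity and seriousness are what is at risk.
- Section 8.3.9 opens with no relatedness limit and asks for a relatedness assessment in each report; the synopsis and SAP 10.6 record all SAEs. Reasons for discontinuation are also summarized and listed (Protocol 9.4.2, SAP 10.2.1), so a death leading to discontinuation would probably appear there. This stands against any claim that unrelated SAEs are excluded by rule. It does not remove the conflict.
- Between-arm bias is not shown. Three of the four events in the 10–20% group of the Apligraf list (Protocol 2.3.1) are away from the study site. That suggests the affected class may be common. But such events could be called unrelated in every arm, which points to under-description rather than a false difference.
- The declared safety endpoint concerns product-, procedure- or wound-related events in a post-market study, so concentrating detail on related events is largely consistent with it. This stands in part. The full-information rule in 8.2 names product and procedure but not the wound, so an ulcer event attributed to underlying disease could fall within the endpoint and still carry dates only. And the SAP's tables go beyond the endpoint.

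**Conclusion.** The point holds as a contradiction that affects safety capture. Protocol 8.2, 8.3.1, 8.3.9 and 9.4.7 do not agree among themselves, or with the synopsis and SAP 10.6 and 10.7. A site and a statistician could each follow the documents and work to different rules.

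The loss of coding and grading for unrelated events is conditional: it follows if the dates-only sentence governs and the eCRF collects no more than that. The omission of unrelated SAEs or deaths is likewise a possibility, open to a site that follows the narrower sentence of 8.3.9. Distortion between arms is a risk of unknown size and direction; the 8 to 24 points above rest wholly on assumed inputs. The matter should be corrected, since the remedy is cheap.

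**What to change.** - **Protocol 8.2:** state that term, seriousness, severity, relationship, action and outcome are recorded for every AE in the collection period that the protocol sets. State that period once: 8.2 starts after the first screening visit, 8.3.1 at first randomized treatment, and 8.3.7 at consent.
- **Protocol 8.3.9 and 9.4.7:** state that all SAEs and deaths are recorded and reported regardless of relatedness, as in the synopsis and SAP 10.6.
- **Protocol 8.3.1:** remove relatedness from the AE definition so that its two sentences agree.
- **If collection is already complete**, which SAP section 12 suggests is possible because it describes the photograph review as done: state in the SAP which fields exist for unrelated events, limit or label the 10.7 tables to events that have them, and query sites for SAEs and deaths judged unrelated.

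The cost is slightly more eCRF entry per unrelated AE and a few wording changes or, after collection, one round of site queries and narrower tables.

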8.3 ADVERSE EVENTS AND SERIOUS ADVERSE EVENTS

8.3.1 DEFINITION OF ADVERSE EVENT (AE)

For the purposes of this research protocol, an **adverse event** means any untoward medical occurrence or adverse reaction (AR) associated with the use of an intervention in humans, that is considered possibly, probably, or definitely-related to the investigational product or study procedure. All events starting or worsening after the first randomized treatment through study exit will also be collected.

8.3.2 DEFINITION OF INVESTIGATIONAL PRODUCT

Investigational Product is defined as either the AMNIOEXCEL Plus or Apligraf allograft.

8.3.3 DEFINITION OF STUDY PROCEDURE

Study Procedure is defined as the application of any of the SOC products used in the care of the wound and/or sharp debridement.

8.3.4 DEFINITION OF ADVERSE REACTION

An Adverse Reaction is defined by the FDA as any noxious or unintended response for which there is a reasonable possibility that the HCT/P caused the reaction. This includes, but is not limited to, the transmission of communicable diseases or infectious agents such as viruses, bacteria, or fungi, or allergic reaction. In addition to your normal adverse event reporting procedures in this study, adverse reactions should be reported within 2 business days to a Sponsor representative. This person can either be the Clinical Research Manager, the Clinical Research Associate assigned to the site, or the Medical Monitor. In this study, only those subjects randomized to receive AMNIOEXCEL Plus may experience an adverse reaction as it is the only HCT/P used in this study.

8.3.5 DEFINITION OF SERIOUS ADVERSE EVENT (SAE)

An adverse event is considered "serious" if, in the view of either the investigator or sponsor, it results in any of the following outcomes:

- Death,
- a life-threatening adverse event,
- inpatient hospitalization or prolongation of existing hospitalization,
- a persistent or significant incapacity or substantial disruption of the ability to conduct normal life functions, or
- a congenital anomaly/birth defect.

8.3.5.1 SUB-DEFINITIONS OF SERIOUS ADVERSE EVENT COMPONENTS

- **Death** - If it is suspected that the death was an outcome of the adverse event
- **Life-threatening** - If it is suspected that the subject was at substantial risk of dying at the time of the adverse event, or use / continued use of the investigational (study) device or study procedure might have resulted in the death of the subject.
- **Hospitalization (initial or prolonged)** - If subject admission to the hospital or prolongation of hospitalization was a result of the adverse event. Emergency room visits that do not result in admission to the hospital should be evaluated for one of the other serious outcomes (e.g., life-threatening; required intervention to prevent permanent impairment or damage; other serious medically important event).
- **Disability or Permanent Damage** - If the adverse event resulted in a substantial disruption of a person's ability to conduct normal life functions, i.e., the adverse event resulted in a significant,

persistent or permanent change, impairment, damage or disruption in the subject's body function/structure, physical activities and/or quality of life.

- **Congenital Anomaly/Birth Defect** - If it is suspected that exposure to the investigational (study) device or study procedure prior to conception or during pregnancy may have resulted in an adverse outcome in the child.
- **Required Intervention to Prevent Permanent Impairment or Damage** - If it is suspected that medical or surgical intervention was necessary to preclude permanent impairment of a body function, or prevent permanent damage to a body structure, either situation suspected to be due to the use of the study intervention or study procedure
- **Other Serious Important Medical Events** - When the event does not fit the other outcomes, but the event may jeopardize the subject and may require medical or surgical intervention (treatment) to prevent one of the other outcomes. Examples include allergic bronchospasm (a serious problem with breathing) requiring treatment in an emergency room, serious blood dyscrasias (blood disorders) or seizures/convulsions that do not result in hospitalization. The development of drug dependence or drug abuse would also be examples of important medical events.

Note: Planned hospitalization for a pre-existing condition, or a procedure required by the clinical study protocol, without serious deterioration in health, is not considered a serious adverse event.

8.3.6 CLASSIFICATION OF AN ADVERSE EVENT

8.3.6.1 SEVERITY OF EVENT

For adverse events (AEs) not included in the protocol defined grading system, the following guidelines will be used to describe severity.

- **Mild** – Transient or mild discomfort; no limitation in activity; no medical intervention or therapy required. The subject may be aware of the sign or symptom, but tolerates it reasonably well.
- **Moderate** – A moderate limitation in activity, minimal medical intervention and/or therapy is required to provide relief and/or resolution.
- **Severe** – A marked limitation in activity; advanced medical intervention and/or therapy, possibly including hospitalization was required to provide relief and/or resolution.

8.3.6.2 RELATIONSHIP TO STUDY INTERVENTION

Relationship of all AEs to the investigational product, the comparator, or study procedure may be classified according to the following classifications/definitions.

- **Not Related:** The AE is due to an underlying or concurrent illness or the effect of another device, another drug or another intervention and is not related to the study device and/or study procedure (i.e. clearly not related).
- **Unlikely:** The relationship with the use of the investigational product or procedures seems not relevant and/or the event can be reasonably explained by another cause, but additional information may be obtained.

- **Possibly Related:** The AE occurred in a reasonable time period relative to use of the investigational product and/or study procedure, which makes a causal relationship possible, but an alternative etiology is equally or less likely compared to the potential relationship to the investigational product and/or study procedure (i.e., may be related).
- **Probably Related:** The AE occurred in a reasonable time period relative to use of the investigational product and/or study procedure, and another etiology is unlikely or significantly less likely, which makes a causal relationship probable (i.e. likely related).
- **Related:** The AE occurred in a reasonable time period relative to use of the investigational product and/or study procedure and has a known relationship to the study device and/or study procedure, or is the only etiology available, making the causal relationship certain (i.e., clearly related).

8.3.6.3 EXPECTEDNESS

Study Investigators will be responsible for determining whether a product or procedure-related SAE is “anticipated” or “unanticipated”. A product or procedure-related SAE will be considered unexpected if the nature, severity, or frequency of the event is not consistent with the risk information previously described for the study intervention.

In determining expectedness of a SAE, the Investigator should consult the following:

- Previous experience with the product or procedure
- Literature provided with any treatments (AMNIOEXCEL Plus; Apligraf product inserts)

[figure not shown]
Although every adverse event occurring in an individual may be considered unanticipated, for the purposes of this study, anticipated events are those which are known to commonly occur in individuals with diabetes and DFUs. Although every adverse event occurring in an individual may be considered unanticipated, for the purposes of this study, anticipated events are those which are known to commonly occur in individuals with diabetes and DFUs. Those events include but are not limited to:

- Ulcer enlargement, tunneling and/or undermining
- Malodor
- Erythema
- Edema
- Maceration
- Excessive drainage
- Development of a new ulcer,
- Ulcer infection or abscess,
- Osteomyelitis
- Trauma/falls and/or
- Amputation

Although these remain adverse events, they are considered “anticipated”. The following diagram (Figure 3) is to assist in the expectedness determination:

[See Next Page for Diagram]

Figure 3: Expectedness Determination of Investigational Product or Procedure-Related SAEs

